1.1. Synopsis

Protocol Title:

Feasibility and Acceptability of Click's EMA and text message intervention for STRESS management (FACE STRESS study).

Rationale:

The purpose of the proposed study is to explore feasibility, acceptability, and initial efficacy of an Ecological Momentary Assessment (EMA) and text message intervention for stress management.

Objectives and Outcomes

Objectives	Outcomes
Primary	

 • Feasibility of recruitment including eligibility rates and acceptance rates • Feasibility of delivering the intervention via text message • Acceptability of the intervention including dropout rates, percentage of completed assessments, adherence, and estimates of satisfaction 	
The main outcome of the FACE STRESS study is to evaluate feasibility and acceptability of an EMA and EMA plus text message intervention. Specifically, we will evaluate:
 
 • number of interested individuals who contact Click Therapeutics because their interest in participating in the study • the number of eligible individuals after the initial screening • time taken to recruit the sample • retention rates • the number and percentage of participants responding to any EMA text over the 3-week study • Satisfaction will be measured using both open-ended questions and likert-scaled questions to examine the

	acceptability and utility of the both EMA and intervention texts.
Secondary	

 Explore indicators of the EMA and text message intervention efficacy The effect sizes on reductions in perceived stress and other psychological symptoms will be estimated in the EMA and EMA+ intervention groups at post-intervention, 1, 3 and 6-month time-points. 	Secondary outcomes will measure: 
 Perceived stress and psychological overload symptoms of anxiety and depression symptoms of PTSD positive and negative affects resilience psychological well-being

Overall Design:

Brief Summary:

The purpose of this study is to evaluate feasibility and acceptability of an EMA compared with an EMA plus text message intervention in participants with higher-than-average perceived stress.

Study details include:

Study Duration: 7 months

Intervention Duration: 3 weeks

Number of Participants: 70

Up to 120 participants will be screened to achieve 70 enrolled to the study (see Section 9.2).

Groups and Duration: 2 groups (EMA alone or EMA plus text message intervention); 3 weeks

Data Monitoring Committee/Data Safety Monitoring Board: N/A

1.2. Schema

N/A

1.3. Schedule of Assessments (SoA)

Procedure	Pre-Enrollment	Day 1	Days 2-4	Days 5-25	Day 26	1 Mo. Post-Study	3 Mos.	6 Mos.	E/D ¹
Telephone Contact	X								X
Inclusion and Exclusion Criteria	X								
Demography	X								
Informed Consent		X							
Baseline Assessment			X						
EMA+Intervention				X					
Post Intervention Assessment					X				
Follow Up Assessment						X	X	X	

Protocol DL-FACE-101 v1.0

Procedure	Pre-Enrollment	Day 1	Days 2-4	Days 5-25	Day 26	1 Mo. Post-Study	3 Mos.	6 Mos.	E/D ¹
AE/SAE Reporting		X	X	X	X	X	X	X	X
1. Early Discontinuation									

2. Introduction

Click Therapeutics digital therapeutic software applications are integrated with the unique feature of a personalized messaging system. Personalized messages provide the opportunity to tailor the intervention to the specific needs of the individual patient. This study will be pivotal in addressing the feasibility of adding to Click's platform a stand-alone text message intervention for stress management. Many patients with psychiatric and medical conditions suffer with chronic stress which exacerbate course and progression of the disease. A stand-alone text message intervention will represent an important feature to add to Click's platform across indications to target patients with high levels of stress.

2.1. Study Rationale

The overarching goal of Face Stress study is to explore feasibility and acceptability and initial efficacy of an EMA and text message intervention for stress management as a digital intervention. As the current pandemic has the potential of causing an increase in mental health problems in people who will be affected by Covid-19 for various reasons and in-person counselling and support are not possible, evaluating the feasibility of using a text messaging intervention to manage stress could be the stepping stone to provide support and reach a broader population. Based on this premise, our main research questions are: 1) Will it be feasible to deliver an EMA and text message intervention for the management of stress?; 2) Will participants find the EMA delivery and SMS content acceptable (satisfactory); 3) Efficacy question: will the text message intervention result in improved resilience and/or reduced psychological distress?

2.2. Background

The covid-19 pandemic represents an historic event with the potential to cause enormous psychological distress both because of the fear of the virus and its health implications, and because it requires major life adjustments (i.e. social distancing, isolation, unemployment etc.) which pose further strain on people's mental health. A recent review of the available literature reported that in the general population symptoms of distress and self-reported stress (8-28%) are common psychological reactions to the COVID-19 pandemic. A survey including 52,730 participants living in the Wuhan region in China, found that 35% of the respondents experienced psychological distress.

How individuals respond to stressful and traumatic experiences over time have been evaluated in longitudinal studies aiming at identifying stress and resilience trajectories. Evidence supports an adapting response with most individuals showing patterns of resilience and gradual recovery (3). However, about 38% of people experiencing traumatic and stressful situations show persistent chronic stress or a delayed stress response. Even though these studies have been helpful in pointing out that most people are indeed resilient, they present several limitations due to the use of traditional assessment methods. Such measures are collected infrequently and require participants to recall past events, feelings, and states, increasing the likelihood of bias and

limiting the ability to detect points of inflection where actual change occurs. Thus, little is known about specific turning points in these trajectories and possible predictors of such turning points in both observational and interventional studies.

Ecologically valid assessment methods have been developed to address the issues represented by the customary recall measures. Ecological Momentary Assessment (EMA) involves measuring psychological processes repeatedly in real time as they occur in the natural environment. EMA encompasses diverse assessment techniques including diaries, behavioral observation, and self-monitoring. EMA presents the advantage of minimizing recall bias, while improving generalizability and ecological validity. It also allows the identification of microprocesses that influence behaviors in real-world contexts.

Several contributions reported that during the 2003 SARS epidemic, individuals who presented high levels of stress continued showing stress symptoms longer after the successful containment of the disease. A survey conducted on the general population, 4 months after resolution of the SARS crisis in Taiwan found that the prevalence of psychiatric morbidity was 11.7%. Lee et al. (7) showed that SARS survivors not only had higher stress levels during the outbreak, compared with control subjects (PSS-10 scores = 19.8 and 17.9, respectively; $P < 0.01$), but this also persisted 1 year later (PSS-10 scores = 19.9 and 17.3, respectively; $P < 0.01$). At 1 year, about 64% of participants scored above the GHQ-12 cut-off suggesting the presence of psychiatric morbidity (7). Health care workers had stress levels similar to those of non-health care workers, but showed significantly higher stress levels a year later (PSS-10 score = 22.8, compared with PSS-10 score = 18.4; $P < 0.05$) and had higher depression, anxiety, posttraumatic symptoms, and GHQ-12 scores (7). Likewise, individuals who had been quarantined, or worked in high-risk locations such as SARS wards, or had friends or close relatives who contracted SARS, were 2 to 3 times more likely to have high PTSD symptoms, than those without these exposures 3 years later. In the light of these findings and the knowledge that about 1/3 of individuals affected by stressful life events show a chronic or delayed stress trajectory, we can assume that, without intervening, millions of survivors in the 216 countries affected will progress to develop psychiatric morbidity.

To overcome the actual challenge of delivering counseling and psychological support in person, text messaging interventions could represent a convenient and easy solution to adopt. Text message interventions have been widely used to support healthy behavior change such as smoking cessation, weight loss and health promotion. Evidence shows that text messaging interventions are effective in promoting behavior change. For example, a three-arm randomized trial compared self-reported alcohol use three months after emergency department visits, during which 765 young adults reported hazardous drinking. The number of self-reported binge drinking days decreased from baseline to three months in the real-time feedback group compared to text message drinking assessments without feedback or a control condition. A health text-messaging program including a range of health topics and information was effective in increasing health awareness in college students. Previous research provided evidence that text messages intervention including psychoeducation, reminders, and links to informative materials can be effective in improving individuals' mental health. For example, a text message intervention was found to be effective in improving parental competence and parental distress (estimated mean difference, -2.39 points; 95% CI, -4.37 to -0.40 points; $P = .02$) compared to

controls. Agyapong et al sent supportive text messages twice a day to a sample of 54 patients with depressive symptoms over a 3-month period. During this period, patients in the intervention group had significantly lower scores on the Beck Depression Inventory-II than control groups (8.5, standard deviation [SD] 8.0 vs. 16.7, SD 10.3, $P=.003$). In Canada, a supportive text message (Text4Mood) program was recently launched to support mental health during COVID-19. Within 1 week of the launch of Text4Hope, 32,805 subscribers had signed up to the program showing the relevance and timely importance of text messaging intervention.

2.3. Benefit/Risk Assessment

Some participants may experience discomfort when completing assessments related to their stress levels and emotional well-being. Although participation in this study may reduce stress and improve emotional well-being, we recognize that individuals experiencing high stress may conversely face the risk of symptomatic worsening. Both text message platforms are two-way. This will allow for review of the evaluation of content and assessment to determine if participants are experiencing a worsening of stress and are in need of further support.

3. Objectives and Endpoints

Objectives	Outcomes

Primary
 
 • Feasibility of recruitment including eligibility rates and acceptance rates • Feasibility of delivering the intervention via text message • Acceptability of the intervention including dropout rates, percentage of completed assessments, adherence, and estimates of satisfaction 	
The main outcome of the FACE STRESS study is to evaluate feasibility and acceptability of an EMA and EMA plus text message intervention. Specifically, we will evaluate:
 
 • proportion of individuals who will contact us because interested to participate • the number of eligible individuals after the initial screening • time taken to recruit the sample • retention rates • the number and percentage of participants responding to any EMA text over the 3-week study • Satisfaction will be measured using both open-ended questions and likert-scaled questions to examine the acceptability and utility of the both EMA and intervention texts.

Secondary
 
 • Explore indicators of the EMA and text message intervention efficacy The effect sizes on reductions in perceived stress and other psychological symptoms will be estimated in the EMA and EMA+intervention groups at post-intervention, 1, 3 and 6-month time-points. 	
Secondary outcomes will measure:
 
 • Perceived stress and psychological overload • symptoms of anxiety and depression • symptoms of PTSD • positive and negative affects • resilience • psychological well-being

4. Study Design

4.1. Overall Design

This study is a pilot randomized controlled trial with embedded qualitative research. Eligible participants who complete an informed consent form will be randomized to receive 3 weeks of EMA or 3 weeks of EMA plus the text message intervention for stress management based on a 1:1 allocation using random block sizes of 2.

Eligible participants will sign the consent form online before moving on to complete their baseline assessment. All participants will receive a copy of their signed consent form and will be provided with the research personnel's contact details. Participants who do not complete the baseline survey within 3 days from enrollment will be excluded from the study. Once their baseline is completed, participants will be randomized to receive:

- **Control:** 3 weeks of EMA, consisting of 2 text messages per day delivered at random times during waking hours to prompt participants to complete the survey
- **Intervention:**
 - o 1 week of EMA, consisting of 2 text messages per day delivered at random times during waking hours to prompt participants to complete the survey followed by
 - o 2 additional weeks of EMA in combination with 2 text messages per day with content related to stress management techniques.

At the end of the 3 weeks, participants in both groups will complete a post-intervention survey designed to evaluate participant satisfaction and to gather information for the purposes of improving the content of the text-message intervention. Changes in levels of psychological distress and well-being from baseline will be also evaluated.

At 1, 3 and 6-months post intervention, participants will be contacted via text message to complete a follow up survey. The follow up survey will include the same information collected at baseline with the exclusion of age, race, gender and adverse childhood events.

Participants from either group will be informed that they can withdraw from the study at any time without giving a reason by replying 'STOP' to any of the messages, or by contacting a member of the research team. No further information will be collected from participants who withdraw from the study.

Participants in the control group will be offered the opportunity to receive the intervention after the 6 months follow-up period. No data will be collected from this intervention.

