4.3. End of Study Definition

The end of trial date is defined as the date at which all subjects have completed all activities shown in the Schedule of Assessments, all data has been entered, all data queries have been resolved, and the database has been locked.

5. Study Population

70 participants will be randomized to control (n=35) or intervention group (n=35)

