6.3. Measures to Minimize Bias: Blinding

N/A

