9.2. Sample Size Determination

Based on an expected small to moderate effects size (17) of the text message intervention for stress management, a sample size of 70 participants (35 participants per arm) will be sufficient to establish feasibility for a 80% powered main trial with an 80% upper confidence limit (18). About 120 participants will be screened to achieve up to 70 enrolled to the study.

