9.3. Analysis Sets

9.4. Statistical Analyses

Primary outcome.

- *Quantitative analysis.* Feasibility of the intervention will be reported as descriptive statistics, focusing on number of individuals who contact the study team with interest in participation; the number of eligible individuals after the initial screening; time taken to recruit the sample; retention rates; the rate of EMA survey completion. Acceptability will be measured as means and standard deviations of responses to each item within the satisfaction questionnaire, and the proportion of participants giving favorable responses.
- *Qualitative analysis.* A codebook and coding guidelines will be developed for analysis of qualitative feedback. Two researchers will code all transcripts using [REDACTED] and add to the codebook as needed. Each researcher will then independently identify main themes. Results will be compared and discussed until an agreement will be reached. Representative samples of feedback from open-ended questions will be also used.

Secondary outcomes.

- *Standard responses.* Sociodemographic responses will be described by mean, standard deviation (SD), and range. Mixed-effects models for repeated measure (MMRM) will be used to examine change in secondary outcomes, with outcomes examined as change in scores between baseline and follow-up. Models will include effects for time, group (control/intervention), group x time interactions and baseline values of the outcome variable (to control regression to the mean) and other potential confounders. Per Protocol analysis will be performed. The per protocol population will include all randomized participants excluding those who had protocol violations. A significance level of 0.05 will be used. All analyses will be performed using [REDACTED]

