10.1.4.1. Medical Monitor

- Participant safety will be continuously monitored by the Medical Monitor, which includes safety signal detection at any time during the study.
- All safety data collected will be summarized and reviewed by the Medical Monitor for agreement of next steps.
- If at any time during the course of the study, the PI judges that risk to subjects outweighs the potential benefits, either shall have the discretion and responsibility to recommend that the study be terminated.
- Case unblinding may be performed for above reviews if necessary.

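### The block scheme names one fixed size, 2, and no concealment is described: anyone who sees earlier allocations knows every second assignment, 35 of 70, before it is made.

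*Combined protocol and SAP*

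**What the plan says.** Section 4.1 describes a pilot randomised controlled trial with allocation "based on a 1:1 allocation using random block sizes of 2". Section 5 gives 70 randomised, 35 to each arm. No stratification is mentioned.

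On sequence, Section 4.1 places online consent first, then the baseline survey, then randomisation: "Once their baseline is completed, participants will be randomized to receive" one of the two arms. Between consent and randomisation there is a time rule: "Participants who do not complete the baseline survey within 3 days from enrollment will be excluded from the study".

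Section 6.3, headed "Measures to Minimize Bias: Blinding", contains only N/A. Section 10.1.4.1 nevertheless allows for a blind to be broken: "Case unblinding may be performed for above reviews if necessary".

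Arms are compared in Section 9.4, where the repeated-measures analysis of the secondary outcomes is specified: "Models will include effects for time, group (control/intervention), group x time interactions", plus the baseline value and other potential confounders, at a 0.05 significance level.

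**The concern.** Block sizes can be random only if at least two sizes are possible. If the phrase is loose wording for randomly permuted blocks of 2, the result is the same: each pair is either control then intervention or the reverse, and the first member determines the second.

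Such a list is harmless if nobody involved in enrolment can see it or the allocations already made. The readable text does not say who generates or holds the list, whether release is automated, or whether staff who screen, enrol or handle baseline completion can see earlier allocations. Section 6.2 has text send times recorded, and Section 6.4 requires a record of the intervention given to each participant, so records that reveal the arm will exist.

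The likeliest opening is the interval of up to 3 days between consent and baseline completion, because that step decides who is randomised and in what order. Phone screening is a weaker route, since a person's place in the sequence is fixed only later. A steered sequence would make the arms differ in motivation or likely adherence. That would bias the secondary comparisons, which rest on self-reported outcomes, and retention and satisfaction by arm. Adjustment for baseline scores would reduce this bias but could not exclude it. The descriptive recruitment counts would be little affected.

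**Working it through.** **Inputs.** 70 randomised, 35 per arm (Section 5); 1:1 allocation in blocks of 2 (Section 4.1); EMA only in both arms during week 1 (Section 4.1). Assumed: one unstratified sequence.

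**Plan's own figure.** 70 / 2 = 35 complete blocks with one participant per arm in each, so exactly 35 per arm. This reproduces Section 5.

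**Blocks of 2.** Let q be the share of earlier allocations that an observer can see.

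- Certain: half of all places are second in a pair, and each is known if the first was seen, so the certain share is 0.5q.
- Correctly guessed: 0.5 × 0.5 + 0.5 × [q + (1 − q) × 0.5] = 0.5 + 0.25q.

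| q | Certain | Correctly guessed |
|---|---|---|
| 1 | 50% (35 of 70) | 75% (52.5 of 70) |
| 0.5 | 25% (17.5 of 70) | 62.5% |
| 0 | 0 | 50% |

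**Other fixed sizes, all earlier allocations visible** (exact enumeration). For blocks of 4 there are 6 arrangements. Two of them force the last two places and four force only the last, so the certain share is (2 × 2 + 4 × 1) / 6 / 4 = 33.3%; correct guesses are 70.8%. For blocks of 6 the figures are 25.0% and 68.3%.

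**Sizes 4 and 6 mixed at random** (equal probability, 20,000 simulated lists of 70, an observer who knows the two sizes, sees all earlier allocations and guesses optimally): 5.5% certain, 69.1% guessed. The final split is 35/35 in 76.7% of lists and 36/34 in 23.3%. It cannot be worse: stopping at 70 cuts the last block, if at all, after 2 or 4 places, and neither cut can leave a difference above 2.

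**Could the arm be inferred from delivered texts alone?** Content messages start only after week 1, so any inference lags randomisation by 7 days. With 70 uniformly spread entry times (4,000 runs; recruitment period assumed), the mean number of certain assignments is:

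| Recruitment period | Certain assignments of 70 |
|---|---|
| 2 to 8 weeks | 0.0 |
| 12 weeks | 0.1 |
| 20 weeks | 1.0 |
| 26 weeks | 2.3 |

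The exposure therefore comes from access to the list or the platform, not from watching messages.

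**Weight of one participant.** 1 / 35 = 2.9 percentage points of an arm's retention. This is a scale for reading the result, not an estimate of bias.

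**The case against.** The 50% figure is a worst case. It needs someone who sees every earlier allocation in order, knows or infers the block size, and can influence who comes next. No section describes such a person. Consent and baseline are completed online, the 3-day limit is a fixed rule, and randomisation after baseline already closes part of the route. The nearest text to staff involvement is the statement in Section 8 that staff review surveys for completeness. Allocation may well be automated and concealed in practice. Some text is removed from Sections 5.5, 6.1 and 6.2, although those sections deal with recruitment, message development and the messaging platform. The trial is a pilot with descriptive primary outcomes, and no bias in any outcome has been quantified. Finally, once earlier allocations are hidden, block size matters little, and blocks of 2 guarantee 35/35.

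Much of this stands. The steering route is inferred, not documented; the size runs from 0 to 35 certain assignments depending on access; and concealment matters more than block size. The unblinding sentence in Section 10.1.4.1 is a side issue, since blinding after allocation is different from concealing the allocation.

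It does not remove the problem. The plan states a rule that is predictable as written, gives no readable safeguard, and then tests between-arm effects at 0.05. Varying sizes also have value as a second line of defence: if earlier allocations do become visible, the certain share is about 6% instead of 50%.

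**Conclusion.** The concern holds. As written, the scheme is fixed pairs, and its protection rests on concealment that the readable text does not describe. With full visibility of earlier allocations, 35 of 70 assignments are certain and 75% can be guessed; with none visible the figures are 0 and 50%. These figures assume a single unstratified list and an observer who knows the block size. Unstated stratification would mean tracking within strata, but every complete pair would still contain one forced assignment.

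This is a correctable weakness in the between-arm comparisons. It is not fatal to a feasibility pilot, and nothing here suggests that steering took place. The change should be made because the remedy is cheap.

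**What to change.** Replace the allocation wording in Section 4.1 with text along these lines: permuted blocks of randomly varying size (4 and 6), with the block sizes, the sequence and past allocations withheld from staff who screen, enrol or follow up baseline completion, and each allocation released by the system only after the baseline survey is submitted. Randomisation after baseline is already planned; the additions are the varying sizes and the withholding, of which the withholding matters more. If allocation is already automated and concealed, the sponsor need only say so and correct the block wording.

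Also reconcile the N/A in Section 6.3 with the unblinding provision in Section 10.1.4.1 by stating who, if anyone, is kept unaware of the arm.

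The cost is one sentence, a new computer-generated list and an access restriction on the allocation record. The downside is a final split of 36/34 instead of 35/35 in about 23% of lists, and never worse at 70 randomised.
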